# **FULL PROTOCOL TITLE: The Impact of Contact Lens Coefficient of Friction (CoF) on the Development of Lid Wiper Epitheliopathy (LWE)**

## **1.0 Objectives**

The primary study objectives are to determine the amount of Lid Wiper Epitheliopathy (LWE) induced in subjects after contact lens fitting that do not have LWE at study enrollment. Subjects in the trial will be fit in 2 contact lenses with different coefficients of friction (CoF). One eye will be fit in a contact lens with a low coefficient of friction (Acuvue Oasys®, Johnson & Johnson Vision, Jacksonville FL) while the contralateral eye will be fit in a contact lens with a high CoF (Air Optix® Night & Day® Aqua, Ft. Worth, TX), as reported in the scientific literature. The eye receiving each lens will be assigned randomly. The presence of LWE will be assessed at 2 different time points:

- Approximately 2 hours after contact lens fitting and
- After 7( $\pm 2$ ) days of contact lens wear

**Study Hypotheses:** Contact lenses with a greater coefficient of friction will induce a greater amount of LWE than contact lenses with a lower coefficient of friction. The presence of LWE will be assessed at 2 different study time points. As such, the following hypotheses will be tested:

After one week of contact lens wear

- $H_{01}$ : There is no statistically significant difference in the amount of LWE between contact lenses with different coefficients of friction
- $H_{a1}$ : There is a statistically significant difference in the amount of LWE between contact lenses with different coefficients of friction

After 2 hours of contact lens wear

- $H_{02}$ : There is no statistically significant difference in the amount of LWE between contact lenses with different coefficients of friction
- $H_{a2}$ : There is a statistically significant difference in the amount of LWE between contact lenses with different coefficients of friction

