## **7.0 Study Endpoints**

The primary study endpoints are as follows:

- Examine the development of LWE post-contact lens fitting at the following time points
  - 1-week post contact lens fitting
  - 2 hours after contact lens fitting

The secondary study endpoints are as follows:

- Examine the level of expression in ocular surface tear MMPs post-contact lens fitting at the following time points
  - Pre-contact lens fitting
  - 1-week post contact lens fitting
  - 2 hours after contact lens fit

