## FULL PROTOCOL TITLE: The Impact of Contact Lens Coefficient of Friction (CoF) on the Development of Lid Wiper Epitheliopathy (LWE)

Korb LWE Grading				
Grading	Description	Height (%)	Width (mm)	Final score (grade)
0	no LWE	<25	<2	<0.25
1	mild LWE	25-50	2-4	0.25-1.00
2	moderate LWE	50-75	5-9	1.25-2.00
3	severe LWE	>75	>10	2.25-3.00

\*Final LWE score is the average of the LWE Height and Width

The tears collected by capillary tubes will be stored at -80°C until luminex multibead analysis. 15 µg of total protein will be analyzed for matrix metalloproteinases (MMP)-1, -2, -7, -9, -10. Pre- and post-contact lens wear concentrations of MMP will be compared for each subject. MMPs are a family of zinc proteases and an increase in MMP expression occurs in response to a wide range of stimuli, including adhesion molecules, growth factors, cytokines and hormones and is associated with ocular surface damage. The correlation coefficient, r, will be determined between LWE and the tear film levels of MMPs.

A  $p \leq 0.05$  will be considered statistically significant.

Layman's Description of Procedures	
Patient demographics	The subjects will be asked questions about their age, sex, race and ethnicity.
History	The subjects will be asked questions about their systemic health, ocular disease and surgical history.
Concomitant Medications	The subjects will be asked questions about their current ocular and systemic medications.
Habitual Contact Lens Information	The subjects will be asked questions about how they use their current contact lenses, such as their current contact lens brand and wear time, as performed during a normal eye exam.
Auto-refraction	A machine will shine light into a subject's eye and will estimate their prescription using different powered lenses without making contact with the eye.
Oculus Keratograph	A machine uses a video camera to determine how long it takes for a subject's tear film to

**FULL PROTOCOL TITLE: The Impact of Contact Lens Coefficient of Friction (CoF) on the Development of Lid Wiper Epitheliopathy (LWE)**

	evaporate and the height of the pooled tears between the lower lid and the ocular surface without making contact with the eye.

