## **FULL PROTOCOL TITLE: The Impact of Contact Lens Coefficient of Friction (CoF) on the Development of Lid Wiper Epitheliopathy (LWE)**

### Addendum: Statistical Analyses

Statistical analyses were performed in SPSS v26 (IBM) and GraphPad. When data were not significantly different from a normal distribution (non-invasive tear break up time, tear meniscus height), statistical analyses were conducted using paired t-tests and repeated-measures analyses of variance (RM-ANOVA), with adjusted post-hoc t-tests, when appropriate. For NITBUT and TMH, the RM-ANOVA included two repeated factors—lens type (Acuvue Oasys and Air Optix Night and Day) and time (baseline, 2 hours post-fitting and 7 days after lens fitting). For data that was not normally distributed (LWE staining), Friedman and Mann-Whitney non-parametric statistics were performed. MMP concentrations were adjusted by multiplying raw values by the dilution factor. Tear film MMP concentrations under the level of detection (LOD) were divided by  $\sqrt{2}$  (Croghan et al. 2003). Outliers in MMP data sets were analyzed using the ROUT function in Graphpad Prism 8.4.1 and were removed prior to analysis.

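### The only two-sample test named for the primary LWE outcome, Mann-Whitney, ignores the pairing of eyes within subjects: if fellow eyes are positively correlated, true type I error falls below 5% and power is lost

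*Combined protocol and SAP*

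**What the plan says.** Section 1.0 (Objectives) sets out a contralateral design: "One eye will be fit in a contact lens with a low coefficient of friction", "while the contralateral eye will be fit in a contact lens with a high CoF", and "The eye receiving each lens will be assigned randomly". The alternative hypothesis, worded identically for 1 week and for 2 hours, is two-sided: "There is a statistically significant difference in the amount of LWE between contact lenses with different coefficients of friction". Section 7.0 makes LWE at those two times the primary endpoint. The note under the Korb grading table in Section 8.0 defines the score: "Final LWE score is the average of the LWE Height and Width". It runs from 0 to 3 in coarse steps, so ties are expected. Section 8.0 sets significance at 0.05, and Section 5.0 aims for 20 completed subjects without a power calculation.

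For tear break-up time (NITBUT) and tear meniscus height (TMH), the Addendum (Statistical Analyses) reports that "statistical analyses were conducted using paired t-tests and repeated-measures analyses of variance (RM-ANOVA", with lens type and time both entered as repeated factors. For the primary outcome it says: "For data that was not normally distributed (LWE staining), Friedman and Mann-Whitney non-parametric statistics were performed". It does not say which of these two tests addresses which hypothesis, and it names no signed-rank or other paired rank test.

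**The concern.** Both primary hypotheses compare two eyes of the same person. Mann-Whitney assumes two independent samples. Non-normal data are a reason to use ranks, not a reason to drop the pairing, and the addendum keeps the pairing for NITBUT and TMH.

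Eyes of one person usually resemble each other. When they do, an unpaired test overstates the variance of the lens difference. Its p-value is then too large and loses its nominal meaning, and a real lens effect is easier to miss. With 20 subjects there is little power to spare. Section 5.0 also intends these data to size a larger trial, so an analysis that ignores the pairing could carry the wrong variability into that calculation.

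**Working it through.** **Inputs from the documents.** 20 pairs (Section 5.0); two-sided hypotheses (Section 1.0); alpha 0.05 (Section 8.0); score 0–3, the mean of a height and a width grade (Section 8.0). The figure of 20 is justified by the central limit theorem, so there is no power statement to reproduce.

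**Assumed, because the documents do not give them.** Between-eye correlation r, SD, and size of the lens effect.

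**Step 1: which contrasts could Mann-Whitney serve?**
- Lens against lens at one visit: paired.
- One visit against another within a lens, as a post-hoc test: paired.
- Neophytes against experienced wearers: independent groups, but no hypothesis, endpoint or analysis compares them.

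No documented contrast fits the test.

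**Step 2: approximate type I error.** With common SD σ and n pairs, the mean lens difference has variance 2σ²(1−r)/n. An unpaired test uses 2σ²/n. Under the null its statistic therefore has variance 1−r, and

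true alpha ≈ 2[1 − Φ(1.96/√(1−r))].

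- r = 0: 0.050
- r = 0.3: 1.96/0.837 = 2.34, alpha 0.019
- r = 0.5: 1.96/0.707 = 2.77, alpha 0.006
- r = 0.7: 1.96/0.548 = 3.58, alpha 0.0003

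Only a negative correlation would inflate it (0.074 at r = −0.2).

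**Step 3: approximate power** for a difference of δ = 0.5 SD, n = 20, r = 0.5. Here δ√(n/2) = 0.5 × 3.162 = 1.581.
- Unpaired test on paired data: Φ((1.581 − 1.960)/0.707) = Φ(−0.536) = 30%.
- Paired test: Φ(1.581/0.707 − 1.960) = Φ(0.276) = 61%.

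**Step 4: simulation with the rank tests.** 4,000 trials per setting, 20 pairs. Three outcome models were used: one continuous, and two Korb-like scores (mean of two 0–3 grades, height and width correlated 0.6 within an eye). In the low-friction eye about 69% or 31% of component grades are zero, for cut-points starting at 0.5 or −0.5 on a standard normal scale. Ranges are across the three models; the difference is on the latent scale.

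| r | Type I error, Mann-Whitney | Power at 0.5 SD, Mann-Whitney | Power at 0.5 SD, signed-rank | Power at 0.65 SD, Mann-Whitney | Power at 0.65 SD, signed-rank |
|---|---|---|---|---|---|
| 0 | 4.8–5.1% | 32–36% | 30–35% | 48–55% | 47–53% |
| 0.3 | 2.2–3.0% | 29–36% | 37–46% | 49–58% | 59–68% |
| 0.5 | 0.8–1.7% | 27–34% | 46–57% | 49–58% | 70–80% |
| 0.7 | 0.1–0.5% | 24–32% | 65–77% | 51–62% | 86–94% |

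The signed-rank type I error stayed between 3.8% and 5.5% throughout, including at r = 0.9.

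**Step 5: a second scoring model.** Latent SD 0.8 grade, scores rounded to 0.25 and limited to 0–3, lens shift 0.5 grade (0.5/0.8 = 0.625 SD). Mann-Whitney against signed-rank:
- r = 0.3: type I error 2.3% vs 5.3%; power 46% vs 58%
- r = 0.5: type I error 0.9% vs 4.6%; power 46% vs 72%
- r = 0.7: type I error 0.1% vs 5.6%; power 45% vs 90%

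These figures correspond to a low-friction latent mean near 1.0 grade, which gives about 14% zero scores. With more zeros at r = 0.5, power is 38–39% vs 59–60% (56% zeros) and 29–32% vs 44–46% (78% zeros).

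**The case against.** The strongest objection is that the addendum never says Mann-Whitney is the lens test. Friedman is a matched test. Run on the two lenses at one visit it would be valid, and run on all six lens-by-time cells it would also respect the pairing. This stands as a point about certainty: the assignment of tests is inferred, on the natural reading that Friedman handles three times and Mann-Whitney two lenses. It does not rescue the text. Friedman across time tests time. Friedman over six cells is an omnibus test that does not isolate either primary hypothesis. Friedman on two lenses reduces to a sign test, with less power than signed-rank (39–50% vs 46–57% at r = 0.5 and 0.5 SD). In each of these cases Mann-Whitney still has no documented independent groups to compare.

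A second objection concerns direction. With positively correlated eyes the test is conservative, so a significant Mann-Whitney result is not undermined. That is right; the damage falls on non-significant results.

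A third is that the size depends on assumed inputs. Subjects with LWE above 0.5 in height or width are excluded at entry (Section 3.0) and the first assessment comes at 2 hours, so many zero scores are plausible and the loss is then smaller. That also stands, but the loss persists with 78% zeros and disappears only when the eyes are uncorrelated.

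Finally, this is a pilot. It nevertheless tests formal hypotheses at 0.05 and is meant to inform a larger trial.

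**Conclusion.** The addendum is wrong as written and must be corrected: it names an independent-samples test for the primary outcome of a fully within-subject comparison.

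For 20 pairs and latent differences of 0.5–0.65 SD, the Step 4 table gives a power loss against signed-rank of about 7–13 percentage points at r = 0.3, 18–28 at r = 0.5 and 32–52 at r = 0.7. These sizes rest on assumed correlations, effect sizes and score distributions. The direction needs only a positive between-eye correlation.

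A non-significant Mann-Whitney result should therefore not be read as evidence that the lenses are alike. For sizing the next trial, the paired design needs about (1−r) times the unpaired per-group number. At r = 0.5, planning a contralateral trial from unpaired variability would roughly double the subjects required (1/(1−0.5) = 2).

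**What to change.** - For each primary hypothesis, compute the within-subject difference in LWE score, high-friction eye minus low-friction eye, at 1 week and at 2 hours. Test it with the Wilcoxon signed-rank test, in an exact or permutation version because of ties.
- Report the Hodges-Lehmann paired difference with a 95% confidence interval, and the SD of the paired differences for sizing the larger trial.
- State in the addendum which test answers which hypothesis. Keep Friedman for change over time within a lens, with signed-rank post-hoc tests.
- The addendum is in the past tense, so label the new result as a correction and report it beside the Mann-Whitney result. If signed-rank was in fact run and misnamed, correcting the text is enough.

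The cost is a short change to the addendum and a re-run in the same software on data already collected.

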### **13.0 Withdrawal of Subjects**

Subjects may withdraw consent to participate in the study at any time. Subjects may be withdrawn from the trial by the study investigators if they are lost to follow up (fail to complete Visit 2 within the allotted time period), become pregnant during the trial, have a study-related adverse event that warrants study withdrawal or they fail to follow the study instructions.

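### The LWE analysis does not say which test answers which question: Friedman over visits cannot place LWE at 2 hours or 1 week, and Mann-Whitney ignores the pairing of eyes

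*Combined protocol and SAP*

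**What the plan says.** Section 1.0 (Objectives) aims to determine the amount of LWE induced after fitting. It sets two null hypotheses, H01 at 1 week and H02 at 2 hours, both worded "There is no statistically significant difference in the amount of LWE between contact lenses with different coefficients of friction". The design is contralateral: "The eye receiving each lens will be assigned randomly". Section 7.0 (Study Endpoints) words the primary endpoints differently: "Examine the development of LWE post-contact lens fitting at the following time points", namely 1 week and 2 hours. Section 2.0 (Background) adds that the speed at which LWE develops is unknown.

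The Addendum (Statistical Analyses) gives LWE one sentence: "For data that was not normally distributed (LWE staining), Friedman and Mann-Whitney non-parametric statistics were performed". It states no factor, levels, follow-up tests, effect estimate or rule for missing visits.

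The same paragraph says more about tear break-up time and tear meniscus height, which section 7.0 does not list as endpoints. For these it names paired t-tests and a repeated-measures ANOVA "with adjusted post-hoc t-tests, when appropriate", with lens type and "time (baseline, 2 hours post-fitting and 7 days after lens fitting") as factors. Section 8.0 sets the significance level: a p-value of 0.05 or less "will be considered statistically significant". No adjustment is stated for the two primary hypotheses.

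**The concern.** The protocol asks two kinds of question about LWE: whether and how much it has developed by each named time, and whether the lenses differ at each of those times. A Friedman test over three visits asks only whether the visits differ somewhere. A significant result could be read as LWE developing by 2 hours when the change came only later, and how early LWE appears is what this pilot wants to learn. Nor does an omnibus p-value supply the size and spread of the change, which section 5.0 needs in order to size a larger trial.

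The between-lens question seems to be left to Mann-Whitney, an independent-samples test, although each subject contributes one eye to each lens.

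**Working it through.** **Plan's own figure.** Section 5.0 gives 20 completing subjects with no effect size, SD or power, so there is no figure to reproduce. The check is therefore on how the named tests behave. Apart from the 20 subjects, the 0-to-3 grade range, the three visits and the 0.05 level, every setting below is assumed.

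**Step 1: which factor Friedman uses.** The three time levels are written only for the ANOVA. LWE evaluation is scheduled at steps 1.1.12, 1.2.5 and 2.7 of the visit table, and Friedman is the rank counterpart of a repeated-measures ANOVA. Three visits is therefore the natural reading, though not a stated one.

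**Step 2: can Friedman over visits place the change in time?** Simulation: 20 subjects, 3,000 trials, subject SD 0.5, visit SD 0.35, grades in 0.5 steps floored at 0, baseline capped at 0.5, shift 0 at 2 hours and 0.4 at 1 week. Each contrast is tested at 0.05/2 = 0.025.

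| Test | Significant |
|---|---|
| Friedman over 3 visits | 77.1% |
| 1 week minus baseline, signed-rank | 61.7% |
| 2 hours minus baseline, signed-rank | 1.6% |

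With steps of 0.25 or 0.5 and a latent mean from 0 to 0.5, Friedman was significant in 84% to 98% of trials and the 2-hour contrast in 3% to 20%. The 2-hour rates above 2.5% reflect regression to the mean: subjects are selected for low baseline LWE, so later grades tend to rise without any lens effect.

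**Step 3: does Friedman over visits test H01 or H02?** Simulation: 20 subjects, 2 lenses by 3 visits, grades in 0.25 steps from 0 to 3, baseline mean 0.25, SD 0.6, shifts of 0.5 at 2 hours and 0.6 at 1 week in both lenses, and no lens difference, so that H01 and H02 are true. Friedman within a lens rejected in about 86%, 95% and 99% of trials at correlations of 0.3, 0.5 and 0.7. A significant result is no evidence of a lens difference.

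**Step 4: Mann-Whitney on paired eyes.** With common variance σ² and correlation ρ between fellow eyes, the variance of a between-eye difference is 2σ²(1 − ρ). An independent-samples analysis works as if it were 2σ². The ratio is 1 − ρ, that is 0.7, 0.5 and 0.3 at the three correlations, so the test is conservative. The same simulation, at two-sided 0.05 per visit, gives:

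| Correlation | Mann-Whitney, no lens effect | Signed-rank, no lens effect | Mann-Whitney power, 0.4 shift | Signed-rank power, 0.4 shift |
|---|---|---|---|---|
| 0.3 | 0.020–0.022 | 0.047–0.048 | 0.510–0.514 | 0.632–0.656 |
| 0.5 | 0.007–0.009 | 0.044–0.049 | 0.509–0.513 | 0.776–0.782 |
| 0.7 | 0.001 | 0.042–0.045 | 0.513–0.518 | 0.932–0.935 |

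**Step 5: complete blocks.** Friedman needs a grade at every visit. If 2 to 4 of 20 subjects in the analysis lacked a Visit 2 grade (assumed; no rate is given), 2/20 = 10% to 4/20 = 20% of the 2-hour grades would leave that test. If only completers are analysed, the loss is zero.

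**Step 6: multiplicity.** Two lenses by two times give four contrasts from baseline, so Holm's first threshold is 0.05/4 = 0.0125. Two unadjusted 0.05 tests of H01 and H02 would carry a familywise error of 1 − 0.95² = 0.0975 if independent.

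**The case against.** A reader might infer that the primary endpoints go untested. The documents do not support that. The LWE sentence also names Mann-Whitney, a two-group test, and the preceding sentence of the addendum likewise joins a two-condition test to an omnibus one. A lens comparison at each visit by Mann-Whitney is the likely meaning, and it would address H01 and H02, though inefficiently.

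A reader might also infer that valid 2-hour data are discarded. That is not shown. Section 13.0 says that subjects who miss Visit 2 may be withdrawn, not that their 2-hour grades are excluded. The target is 20 completers, and a per-visit Mann-Whitney would keep those grades.

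The use of three visits as the Friedman factor is itself inferred. A Friedman test across the two lenses at one visit would be a paired test of that visit's hypothesis. Follow-up tests on LWE may have been done without being mentioned.

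Finally, the 2-hour shift in step 2 was set to zero, so 1.6% is simply a false-positive rate, and the contrast with 77% illustrates what any omnibus test does. That is fair.

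What stands is that the addendum assigns neither test to a question and states no follow-up for LWE, while stating one for measures that are not endpoints. Mann-Whitney does not fit the paired design under the reading most favourable to the plan.

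**Conclusion.** The concern holds in a conditional form. On the natural reading, Friedman over visits bears on the development of LWE only globally: it cannot separate 2 hours from 1 week, gives no amount, and does not test H01 or H02. Mann-Whitney probably tests those two but ignores the pairing. At the assumed 0.4-grade difference this costs between about 0.12 (0.632 − 0.514) and 0.42 (0.935 − 0.518) in power. It does not inflate false positives in the settings tried, where fellow eyes were positively correlated.

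The sizes rest on assumed variances, shifts and correlations. The qualitative conclusions about Friedman do not. Loss of 2-hour data arises only if subjects without a Visit 2 grade are in the analysis set. This is a worthwhile and cheap improvement to a pilot, not evidence that its primary questions went unanswered.

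**What to change.** 1. State which test serves which question.
2. For development of LWE, replace Friedman by planned paired contrasts within each lens: 2 hours minus baseline and 1 week minus baseline. Each should use all subjects graded at both visits, by signed-rank test with a Hodges-Lehmann estimate and interval, Holm-adjusted over the four lens-by-time contrasts.
3. For H01 and H02, replace Mann-Whitney by a paired between-lens signed-rank test at 1 week and at 2 hours. Use all subjects with both eyes graded at that visit, and say how the two tests share the 0.05.
4. Report the changes from baseline with a caution. Exclusion criterion 2 in section 3.0 selects for low baseline LWE, so some rise is expected from regression to the mean. The between-lens contrast is largely free of this, because both eyes pass the same screen and lens is randomised to eye. Step 1.1.12 of the visit table reads the opposite way to that criterion, and the two must be reconciled before the direction of this bias is stated.

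The cost is addendum wording and a re-run on data in hand. The addendum is written in the past tense, so the re-run should be labelled as specified after the fact. Sensitivity is somewhat lower than the omnibus test in most simulated settings: 62% against 77% in step 2, with a threshold of 0.025. Holm's first threshold of 0.0125 would lower it further.

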### **3.0 Inclusion and Exclusion Criteria**

Potential study subjects must meet the following study inclusion criteria:

1. Must be able to read and understand the study informed consent
2. Must be a minimum of 18 years of age and less than 46 years of age at study enrollment
3. Must be healthy non-soft contact lens wearers (neophytes), or experienced contact lens wearers that have not worn their contact lenses for a minimum of 7 days
4. Have a spherical equivalent refractive error between -0.75 to -6.50DS at the spectacle plane
5. The subject must be able to attend study visits at the prescribed visit times and adhere to the study instructions

Potential study subjects cannot meet any of the following study exclusion criteria:

1. Pregnant and/or lactating females by self-report
2. Presence of current LWE on the upper eyelid (>0.5 in height or width)
3. Has greater than -1.00DC of refractive cylinder
4. Has greater than 1.00D of anisometropia
5. Is aphakic
6. Has clinically significant corneal or conjunctival staining that would prevent contact lens fitting, as assessed with sodium fluorescein dye

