### **5.0 Number of Subjects**

The proposed single-site study will be conducted at The Ocular Surface Institute at the University of Houston College of Optometry. Up to 60 subjects will be screened for study inclusion, with the goal of completing 20 subjects. Subjects that screen fail may be rescreened for study inclusion up to 3 additional times at the discretion of the study investigator.

Currently, there is no information on the time from contact lens fitting to the development of LWE. This pilot study is designed to collect data which can be used to determine the sample size required to conduct a larger-scale clinical trial. It is anticipated that enrolling 20 subjects will approach the requirements of the central limit theorem for statistical analysis. Since the subjects in the study will be wearing FDA-approved contact lenses on a daily wear modality (i.e. not sleeping in contact lenses), the study does not present more than minimal risk to the subject and a power analysis is not required.

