1.1.13	Digital Photography	Perform Digital Photography of the Lid Wiper region OD/OS
1.1.14	Subjective Refraction	
Perform Manifest Refraction using maximum plus to best visual acuity.
 
 
• If the subject has <math>> 1.00\text{D}</math> refractive cylinder or greater than 1D of anisometropia, skip to Step 2.9: Final Evaluation and discontinue the subject from the trial
 

1.1.15	Subjective Spherical Equivalent Refraction	Perform Subjective Spherical Equivalent using maximum plus to best visual acuity.
1.1.16	Contact Lens Fitting	
Fit subject in contact lenses based upon the randomization schedule. Initial base curve should be selected as indicated in the fitting guide for each lens.
 
 
• If an acceptable contact lens fit cannot be obtained in either eye, skip to Step 2.9: Final Evaluation and discontinue the subject from the trial
 

1.1.17	Contact Lens Over-Refraction	Perform spherical over-refraction using maximum plus to best visual acuity
1.1.18	Contact Lens Power Adjustment (if necessary)	Modify contact lens power, based upon the Contact Lens Over-Refraction, if the subject gains 3 or more letters acuity
1.1.19	2 hour Waiting Period	Subjects released to waiting area for 2 hours

**FULL PROTOCOL TITLE: The Impact of Contact Lens Coefficient of Friction (CoF) on the Development of Lid Wiper Epitheliopathy (LWE)**

Visit 1.2 Note: Visit should be performed approximately 2 hours after lens insertion		
1.2.1	Visual Performance	Perform logMAR visual acuity
1.2.2	Oculus Keratograph	Perform the following procedures using Oculus Keratograph with the contact lens on eye, OD/OS 
 
• Non-invasive Tear Break Up Time (NITBUT)
 
• Tear Meniscus Height
 
• Video Contact Lens Fit
 

1.2.3	Ocular Surface Tear Collection	Collect 10µL surface tears using a microcapillary tube.
1.2.4	Contact Lens Removal	Remove the contact lenses and store in solution
1.2.5	Slit Lamp Exam with vital dye staining/LWE evaluation	Instill 1 drop of NaFL + Lissamine Green Combination Drop, wait 5 minutes, instill an additional drop, wait 1 minute, then evaluate slit lamp findings using the CCLRU grading scale and evaluate LWE

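### The only two-group test named for LWE treats a subject's two eyes as independent, and no baseline LWE adjustment of the lens contrast is described

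*Combined protocol and SAP*

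**What the plan says.** **Design.** Section 1.0 puts the low-CoF lens in one eye and the high-CoF lens in the other eye of the same person: "The eye receiving each lens will be assigned randomly". Section 5.0 plans up to 60 screened subjects, "with the goal of completing 20 subjects", as a pilot to size a larger trial. It gives no power calculation.

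**Hypotheses.** At 1 week and at 2 hours the null is "There is no statistically significant difference in the amount of LWE between contact lenses with different coefficients of friction". The alternative is non-directional, so the tests are two-sided. Section 8.0 sets the threshold at p ≤ 0.05.

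**Baseline.** LWE is evaluated at Visit 1.1 (Step 1.1.12). Step 1.1.13 then reads "Perform Digital Photography of the Lid Wiper region OD/OS". Exclusion criterion 2 in Section 3.0 is "Presence of current LWE on the upper eyelid (>0.5 in height or width"), so low but non-zero upper-lid grades are admissible.

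**Analysis.** The addendum's only sentence on LWE is "For data that was not normally distributed (LWE staining), Friedman and Mann-Whitney non-parametric statistics were performed". It does not say which test addresses lens and which addresses time, and it names no covariate or change score. For NITBUT and tear meniscus height, by contrast, it declares lens type and time as repeated factors and lists baseline as a time level.

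**The concern.** The two LWE grades in each lens comparison come from the same person, who has one tear film, one blink pattern and one wearing schedule. They are likely to be positively correlated. An independent-samples rank test leaves that shared variation in its error term, although the contralateral design exists to remove it. The addendum respects the pairing for two tear-film measures but, as written, not for the primary outcome.

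With 20 subjects and no power calculation, a non-significant Mann-Whitney result could reflect the choice of test and not the lenses. An unpaired analysis also does not produce the SD of the within-subject difference, which the larger trial needs for its sample size.

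The baseline grade is a second, smaller matter. The objective is LWE induced by wear, and the two eyes of a subject may enter up to 0.5 grade apart. An unadjusted follow-up contrast carries whatever part of that difference persists.

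**Working it through.** The plan offers no figure to reproduce: 20 rests on an appeal to the central limit theorem. The check therefore asks what each analysis does with 20 pairs.

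**Inputs from the documents.** n = 20 pairs; two-sided 0.05; final LWE score from 0 to 3; upper-lid baseline components no higher than 0.5.

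**Assumed inputs.** Follow-up SD 0.6 grade; lens effect 0.35 grade; between-eye correlation r of 0.3 or 0.6; follow-up rising by 0.5 or 1.0 grade per grade of baseline; between-eye baseline correlation 0.5.

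**Step 1: cost of ignoring the pairing (normal approximation).**
- True SE of the lens difference: 0.6 × √(2(1−r)/20), which is 0.159 at r = 0.3 and 0.120 at r = 0.6.
- SE used when the eyes are treated as independent: 0.6 × √(2/20) = 0.190.
- Null rejection rate of the unpaired test: P(|Z| > 1.96/√(1−r)). At r = 0.3 the cut-off is 2.34, giving 0.019. At r = 0.6 it is 3.10, giving 0.002.
- Paired power: Φ(0.35/0.159 − 1.96) = 0.60 and Φ(0.35/0.120 − 1.96) = 0.83.
- Unpaired power: the difference must exceed 1.96 × 0.190 = 0.372, so Φ((0.35 − 0.372)/0.159) = 0.45 and Φ((0.35 − 0.372)/0.120) = 0.43.
- Loss: about 15 and 40 points. At r = 0 there is none.

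**Step 2: simulation on the bounded scale** (2,000 runs per scenario, baseline limited to 0, 0.25 or 0.5). Four of the twelve scenarios, power at a lens effect of 0.35:

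| Baseline, slope, r | Mann-Whitney | Signed-rank | Paired t | Paired, baseline-adjusted |
|---|---|---|---|---|
| mostly 0, 0.5, 0.3 | 0.39 | 0.51 | 0.53 | 0.52 |
| mostly 0, 0.5, 0.6 | 0.37 | 0.75 | 0.77 | 0.75 |
| mixed, 1.0, 0.6 | 0.33 | 0.70 | 0.71 | 0.74 |
| uniform, 1.0, 0.6 | 0.33 | 0.70 | 0.72 | 0.77 |

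Over all twelve scenarios signed-rank exceeds Mann-Whitney by 12 to 39 points. A repeat with a fresh seed gave 12 to 38. Mann-Whitney's null rejection rate is 0.002 to 0.022; signed-rank stays near 0.05.

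**Step 3: what baseline adjustment adds.** Let ρ be the correlation between the baseline and follow-up between-eye differences. Allowing for the estimated slope, the variance factor is about (1−ρ²) × 18/17:
- ρ = 0.1: 0.99 × 1.059 = 1.05
- ρ = 0.2: 0.96 × 1.059 = 1.02
- ρ = 0.3: 0.91 × 1.059 = 0.96

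Break-even is ρ = √(1/18) = 0.24. With baseline confined to 0–0.5, the simulated ρ is 0.10 to 0.37. The power change against the paired t-test is about −2 to +3 points, except for one scenario near +5. The gains of 3 points or more need half or more of the eyes to start above 0, baseline to carry over one-for-one, and r = 0.6. Monte Carlo error on a single power figure is about 1 point (√(0.25/2000) = 0.011).

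**Step 4: chance imbalance.** 1.96 × SD of the between-eye baseline difference / √20 gives ±0.06 grade at SD 0.134 and ±0.13 at SD 0.289.

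**The case against.** **The addendum does not say that Mann-Whitney was the lens test.** This is fair. A Friedman test with lens as a two-level factor would respect the pairing. But Mann-Whitney is the only two-group procedure named, and no paired two-sample rank test is mentioned. If the lens comparison was in fact paired, the wording still has to be corrected.

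**A reader might infer that baseline LWE was discarded altogether.** The text does not support that. Friedman may have run over baseline, 2 hours and 7 days, as the time factor does for NITBUT. What stands is narrower: a Friedman test over time within one lens does not adjust the between-lens contrast, and no such adjustment is described.

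**A reader might infer bias or false positives.** Neither follows. The eye receiving each lens is randomised, so a baseline imbalance is chance and affects precision. With positively correlated eyes, ignoring the pairing makes the test conservative, so a significant Mann-Whitney result is not undermined on this account.

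**A reader might expect a large gain from baseline adjustment.** That needs ρ well above 0.37. Sections 1.0 and 3.0 keep upper-lid baseline near the floor, and 0.5 grade between eyes is the permitted extreme. Two things could change this. Step 1.1.12 as printed continues subjects in whom LWE is observed and discontinues those without it, which contradicts Sections 1.0 and 3.0; these must be reconciled. Section 8.0 also has both lids photographed, while exclusion 2 limits only the upper lid.

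**It is a pilot with no power claim.** True, but it tests two hypotheses at 0.05 and is meant to supply sizing data, and both depend on the within-subject variance.

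**Conclusion.** The concern holds, with the pairing as its main part. As written, the addendum's lens comparison for the primary outcome uses an independent-samples test on contralateral eyes, and it describes no use of baseline LWE in that contrast.

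Under the assumed inputs, pairing recovers about 12 to 38 points of power at 20 subjects. The size depends chiefly on the between-eye correlation, which the documents do not give, and it vanishes at zero correlation.

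Baseline adjustment is worth about −2 to +3 points in nearly all scenarios while baseline is confined to 0–0.5. It would matter more if Step 1.1.12 was followed as printed or if lower-lid LWE is analysed. The baseline part therefore supports a sensitivity analysis and clearer reporting, not a claim that the lens contrast is biased.

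**What to change.** 1. **Lens contrast.** At 2 hours and at 1 week, analyse the within-subject difference in LWE, high-CoF eye minus low-CoF eye, with a Wilcoxon signed-rank test or an ordinal mixed model with a subject effect. Report the estimated difference, its confidence interval and the SD of the paired differences for use in sizing the next trial.
2. **Baseline.** Tabulate baseline LWE by lens. Add the baseline between-eye difference as a covariate, at least as a sensitivity analysis. If every baseline is zero, the term cannot be estimated and is dropped. If only a few are non-zero, those subjects determine the slope, and the report should say so.
3. **Wording.** State the factor and time levels of the Friedman test, which test compares lenses, and whether upper, lower or both lids enter the score. Use one grading source at all times: the Visit 1.2 schedule lists an LWE evaluation but no photography step.
4. **Eligibility.** Reconcile Step 1.1.12 with Sections 1.0 and 3.0 and report which rule was applied.

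The addendum is in the past tense, so this is a re-analysis of data already collected, plus revised text. No new visits or measurements are needed. The covariate costs one degree of freedom.
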